In addition, HDAC has been well-recognized as potential targets for the treatment of numerous aging-related disorders (9) such as cancer (10). Therefore, we plan to evaluate the potential role of biomarkers of aging with the combination of HCQ plus VOR.

These findings support a phase II study VOR/HCQ versus standard therapy RGF in patients failing standard therapies.

We hypothesize that VOR/HCQ will have improved efficacy when compared to RGF in treatment-refractory mCRC patients. This hypothesis is based on the observations that:

1. In refractory mCRC patients, the role of continued VEGF inhibition in mCRC has not been established (4).
2. Only a modest improvement in survival was reported with the use of RGF, an oral multi-kinase inhibitor with predominantly angiogenic inhibition, for mCRC patients who have failed standard therapies (3).
3. Autophagy inhibition enhances vorinostat-induced apoptosis via ubiquitinated protein accumulation in CRC models pre-clinically (5).
4. Clinical activity based on treatment-refractory mCRC patients enrolled in phase I (6) and the ongoing single arm Phase II study of VOR with HCQ therapy suggests a median PFS of > 3 months.

Our overall objective is to answer these questions: will VOR/HCQ be more efficacious than RGF, will VOR/HCQ be safe, and can biomarkers be identified that will predict clinical efficacy of VOR/HCQ and RGF in refractory mCRC patients?

Primary Objective(s):

- To determine the clinical efficacy with progression-free survival (PFS-1) of the combination of VOR plus HCQ when compared to RGF in treatment-refractory mCRC.

Secondary Objective(s):

- To determine the overall survival in refractory mCRC patients receiving VOR plus HCQ when compared to RGF.
- To determine the progression-free survival (PFS-2) of the crossover treatment, which is optional.
- To evaluate the tumor response rate in refractory mCRC patients receiving VOR plus HCQ when compared to RGF.
- To further define the safety of the combination of VOR/HCQ when compared to RGF in treatment-refractory mCRC.
- To identify biomarkers of autophagy and anti-angiogenic inhibition that are associated with clinical efficacy of VOR/HCQ and RGF, respectively, in mCRC.

Primary Endpoint(s):

- PFS-1: measured from the start of the first treatment the patient is randomized to until the date the criteria for progression are met or the date the patient is taken off study for any reason, whichever is shorter.

[figure not shown]
Secondary Endpoint(s):

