3.0 Statement of Study Objectives

Primary Objective:

- To determine the clinical efficacy with progression-free survival (PFS-1) of the combination of VOR plus HCQ when compared to RGF in treatment-refractory mCRC.

Secondary Objectives:

- To determine the overall survival in refractory mCRC patients receiving VOR plus HCQ when compared to RGF.
- To determine the progression-free survival (PFS-2) of the crossover treatment (crossover is optional).
- To evaluate the tumor response rate in refractory mCRC patients receiving VOR plus HCQ when compared to RGF.
- To further define the safety of the combination of VOR/HCQ when compared to RGF in treatment-refractory mCRC.
- To identify biomarkers of autophagy and anti-angiogenic inhibition that are associated with clinical efficacy of VOR/HCQ and RGF, respectively, in mCRC.

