10.0 Statistical Section

Analytic plan for primary objective:

mPFS-1: Historically, the mPFS for previously treated mCRC patients treated with RGF is 1.9 mos. We predict VOR/HCQ will improve mPFS to 3.8 months. We expect 5% lost to followup. Assuming a 36-month accrual period with 1 year for follow up, 36 subjects per group are necessary to obtain 80% power. With 5% lost to follow-up the sample size required per group is 38 ($=36/0.95$), therefore, the total required sample size is 76 subjects. As a result, the target accrual rate is 3-4 patients/month to achieve a target accrual at 36 months with an additional 12month follow-up.

Treatments will be contrasted with regard to PFS-1 with a proportional hazards model with adjustment for age, sex, race, and the baseline tumor K-RAS status (mutated, wild type); the adjusted hazard ratio, its 95% confidence interval, and the p-value for testing the null hypothesis that the log hazard ratio is zero will be presented. Survival curves will be illustrated with Kaplan-Meier plots. Interactions between treatment and baseline covariates will be explored.

If a patient does not complete Cycle 1 and is off study, then this patient will not be evaluable for efficacy but will be evaluable for toxicity.

Interim analysis: The O'Brien-Fleming procedure will be used to conduct an interim analyses for efficacy when 50% of the patients complete the study. A statistical basis for stopping the study at the first look will be achieved if the test statistic indicates benefit in the VOR/HCQ Arm and exceeds 2.96259, corresponding to a significance level of 0.003. If the test statistic does not exceed 2.96259 at the first look then the trial will proceed to the final analysis. A treatment effect will be declared significant and beneficial at the final analysis if the test statistic indicates benefit and exceeds 1.96857, corresponding to a significance level of 0.047. If a treatment effect is not declared at the interim analysis, a statistical basis for stopping the study for futility will be attained if the conditional power is less than or equal to 20%.

Analytic plan for secondary objectives:

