- OS: The analyses of median OS will be performed in the intent-to-treat population. OS will be illustrated with Kaplan-Meier plots, the estimate of median OS with its 95% confidence interval. Treatment groups will be contrasted with regard to the response rate with a logistic regression model adjusted for age, sex, race and the baseline tumor K-RAS status (mutated, wild type); the odds ratio, its 95% confidence interval, and the p-value for testing the null hypothesis that the log odds ratio is zero will be presented. If the logistic model fails due to small cell counts then treatments will be contrasted with regard to response using Fisher's Exact Test.
- mPFS-2: The analyses of median PFS-2 will be performed in the crossover population. Crossover to the other arm will be allowed, but OPTIONAL, and will be determined by the treating physician for the patient's best interest. mPFS-2 will be illustrated with KaplanMeier plots, the estimate of median PFS-2 with its 95% confidence interval. Treatment groups will be contrasted with regard to the response rate with a logistic regression model adjusted for age, sex, race and the baseline tumor K-RAS status (mutated, wild type); the odds ratio, its 95% confidence interval, and the p-value for testing the null hypothesis that the log odds ratio is zero will be presented. If the logistic model fails due to small cell counts then treatments will be contrasted with regard to response using Fisher's Exact Test.
- Response rates: Response rates will be measured as the proportion of patients with the best response, complete response (CR) or partial response (PR), as defined by RECIST 1.1 Criteria and a 95% confidence interval. (See Appendix 13.2 for RECIST 1.1 criteria)
- Adverse events: All adverse events will be listed by type and grade. All adverse events will be listed by treatment group, level of seriousness (serious, not serious). Treatments will be contrasted with regard to each adverse event with Fisher's Exact Test.

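### The comparative safety objective is analysed only by a Fisher p-value per adverse event; adding risk differences with 95% intervals is a cheap improvement, because at about 38 per arm a non-significant p-value could not support a statement of comparable safety

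*Combined protocol and SAP*

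**What the plan says.** Section 3.0 lists as a secondary objective: "To further define the safety of the combination of VOR/HCQ when compared to RGF in treatment-refractory mCRC". The Synopsis also asks more broadly "will VOR/HCQ be safe", without naming a comparator in those words.

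The adverse-events bullet in Section 10.0 has two parts. The first is descriptive: events are listed by type and grade, and then "All adverse events will be listed by treatment group, level of seriousness (serious, not serious"). The second is the only between-arm analysis: "Treatments will be contrasted with regard to each adverse event with Fisher's Exact Test". The bullet gives no risk difference, ratio, confidence interval or significance level, and does not say whether the test is run by grade. The matching Synopsis bullet stops at the listing by type and grade.

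Other endpoints in Section 10.0 get more. For PFS-1 it promises: "adjusted hazard ratio, its 95% confidence interval, and the p-value for testing the null hypothesis that the log hazard ratio is zero will be presented". The response contrast gets an odds ratio with a 95% interval and p-value, falling back to Fisher's test if the logistic model fails. Median OS, median PFS-2 and the response proportion each get a 95% interval.

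On numbers: "With 5% lost to follow-up the sample size required per group is 38". If a patient leaves the study before completing Cycle 1, "then this patient will not be evaluable for efficacy but will be evaluable for toxicity", so about 38 per arm is the relevant size for safety.

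**The concern.** A comparative safety objective needs an estimate of how far the two arms differ and how large an excess the data leave open. A p-value for each event supplies neither. The trial is sized on PFS alone, and the documents state no power or precision for any adverse event. With small counts, p>0.05 is the usual result even when a severe event is truly twice as frequent in one arm. If the table shows only p-values, the reader cannot tell a well-supported absence of difference from a comparison too small to see one.

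**Working it through.** **Inputs**
- n = 38 per arm, 1:1 allocation (Sections 5.0, 5.1 and 10.0).
- RGF grade 3 rates from Section 2.2.1: fatigue 9%, hand-foot syndrome 17%.
- Wider range of RGF grade 3 or higher rates from Section 5.6.3: rash 6% to 7%, palmar-plantar erythrodysesthesia 17% to 22%, hypertension 8% to 28%.
- Two-sided 5% level for Fisher's test. This is an assumption; none is stated for adverse events.

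**The plan's own figure (PFS-1)**
- Medians of 1.9 and 3.8 months give HR = 1.9/3.8 = 0.5 under exponential times.
- Freedman events = [(1+0.5)/(1−0.5)]² × (1.960+0.842)² = 9 × 7.85 = 70.6, so 71.
- With 36 months of accrual and 12 of follow-up, the event probabilities are 0.999 and 0.983 (mean 0.991). Patients per arm = 71/(2 × 0.991) = 35.8, so 36. Then 36/0.95 = 37.9, so 38.
- The stated 36 and 38 per group reproduce. They concern PFS only.

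**Power of the planned safety test**

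Power = Σᵢ Σⱼ Bin(i; 38, p₁) × Bin(j; 38, p₂) × 1[Fisher p(i, j) ≤ 0.05], summed over all tables.

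| Reference rate | Doubled rate | Power | Missed |
|---|---|---|---|
| 6% | 12% | 5.7% | 94.3% |
| 8% | 16% | 10.2% | 89.8% |
| 9% (grade 3 fatigue) | 18% | 12.6% | 87.4% |
| 17% (grade 3 hand-foot) | 34% | 31.4% | 68.6% |
| 22% | 44% | 45.2% | 54.8% |
| 28% | 56% | 62.0% | 38.0% |

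Sensitivity for the 17% and 9% rates: with 37 per arm, 70% and 88% are missed; with a two-sided 10% level, 57% and 80%.

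**What an interval would show (illustrative counts out of 38)**

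The Newcombe interval combines the Wilson limits (l, u) of each proportion: lower limit d − √[(p₁−l₁)² + (u₂−p₂)²], upper limit d + √[(u₁−p₁)² + (p₂−l₂)²]. For 3/38 against 3/38, p = 0.0789 with Wilson limits 0.0272 and 0.2080. The half-width is √(0.1290² + 0.0517²) = 0.139.

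| Counts | Fisher p | Difference in points (95% CI) |
|---|---|---|
| 3 vs 3 | 1.00 | 0 (−13.9 to +13.9) |
| 6 vs 6 | 1.00 | 0 (−16.8 to +16.8) |
| 7 vs 3 | 0.31 | +10.5 (−5.3 to +26.4) |
| 9 vs 3 | 0.11 | +15.8 (−1.0 to +32.2) |
| 13 vs 6 | 0.11 | +18.4 (−1.1 to +36.4) |

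Nine events against three is a threefold observed rate and is still non-significant. Against 3/38, the other arm needs 11/38 before p falls to 0.05 or below (10 vs 3: p = 0.065; 11 vs 3: p = 0.036).

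**The case against.** The strongest reply is that the plan never claims comparable safety. It sets no margin, hypothesis or decision rule, and the objective's verb is to define safety, which is descriptive. That stands. A reader might infer that a non-significant Fisher result would be passed off as comparable safety, but no section says so.

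The broad Synopsis question names no comparator and is served by other means: toxicity stopping rules, six-monthly DSMB review, and off-cycle reporting of any trend of three or more of the same event (Section 8.0). That also stands. Those rules do not compare the arms, however, so they do not serve the comparative objective.

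Listings by arm, grade and seriousness are planned, and incidence and intervals could be derived from them. This is right, and it makes the gap one of planned analysis and presentation rather than of data collection. A reader might also infer that the Fisher test pools all grades; the bullet is silent on this, so grade handling is unspecified.

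The 69% and 87% figures rest on two chosen rates, an assumed alpha and an excess on VOR/HCQ. Hand-foot syndrome is mainly an RGF toxicity, so its doubling on VOR/HCQ is a benchmark for event frequency, not a forecast. Large differences can be detected. As an illustration only, since population, doses and event definitions differ: taking the 54% grade 3 or higher rate on RGF against at most 6 of 31 phase I patients with grade 3 toxicity (Section 2.4.1), power at 38 per arm is about 85%. Non-significance is thus the usual result for doublings of individual severe events at the lower rates, but not for every safety contrast.

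Low power for single events is unavoidable in a 76-patient phase II trial. This is true, and it is the reason to report intervals, not a reason to omit them.

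**Conclusion.** The point holds as a modest improvement to the analysis of a secondary objective. Fisher's test per event is the only between-arm safety analysis, and it comes without an effect estimate or interval, unlike PFS-1 and the response contrast. At about 38 per arm and an assumed two-sided 5% level, a doubling is missed in about 87% of trials at a 9% reference rate and 69% at 17%; over 6% to 28% it is missed in about 94% down to 38%. A non-significant p-value therefore could not support a statement of comparable safety. The documents do not establish that such a statement is intended, that the data collected are inadequate, or that one miss rate applies to all events.

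**What to change.** In the adverse-events bullet of Section 10.0, and in the matching Synopsis bullet:
- Report per-arm incidence (n, N, %) and the between-arm risk difference with a 95% confidence interval, naming the method (for example Newcombe), for each event at any grade and at grade 3-5, and for serious events overall.
- Keep Fisher's p as a secondary descriptor and state its level and sidedness. Near the boundary the two can disagree: 10/38 against 3/38 gives p = 0.065 with an interval of +1.2 to +34.9 points. Say that the interval is the main summary.
- State that p>0.05 will not be taken as evidence of comparable safety.

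Grade and seriousness are already recorded, so this needs no extra patients, visits or data. The cost is a wording change and a few more table columns. The drawback is that the intervals will be visibly wide, about ±14 to ±17 points even when the arms have equal counts of 3 to 6.

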In refractory mCRC, the role of VEGF inhibition in mCRC patients has not been established (30). Recently, Regorafenib (RGF), an oral multi-kinase inhibitor, including with angiogenic inhibition, was approved for mCRC patients who have failed standard therapies (2). In the CORRECT trial, patients with mCRC were randomized in a 2:1 ratio to receive best supportive care with oral RGF 160 mg or placebo by mouth once daily, for 3 weeks of a 4-week cycle (3). The primary endpoint was overall survival. *Compared to placebo, RGF improved mPFS from 1.7 to 1.9 months ($P<0.000001$) and mOS from 5.0 to 6.4 months ($P=0.005$), regardless of K-RAS status (3).* The most common treatment-related toxicities were fatigue (47% vs 28%, RGF vs placebo), hand-foot syndrome (47% vs 8%), diarrhea (34% vs 8%), anorexia (30% vs 15%), voice changes (29% vs 6%), hypertension (28% vs 6%), oral mucositis (27% vs 4%), rash/desquamation (26% vs 4%), nausea (14% vs 11%), weight loss (14% vs 2%), and fever (10% vs 3%). In this study, 54% patients had grade 3 or more adverse events versus 14% with placebo, with the most common grade 3 fatigue (9% vs 5%) and grade 3 hand-foot syndrome (17% vs <1%). In the third-line setting, even when statistical significance is reached, gains in PFS and OS are modest, i.e., 0.2 months (6 days) improvement in mPFS and the 1.4 months (42 days) benefit in mOS seen with RGF over placebo (3). Given the modest improvements of RGF in survival, VEGF inhibition may not be beneficial to all patients with mCRC refractory to VEGF inhibitors; therefore, more therapies are needed in patients with mCRC progressing despite VEGF inhibition.

2.3 Autophagy as a mechanism for cancer survival:

Autophagy is a conserved protein degradation process that involves the vacuolar sequestration of long-lived cytoplasmic proteins and organelles into a structure called an autophagosome (31).

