5.3 Treatment Requirements

All eligible patients who consent to this study must have a baseline evaluation (CT or MRI) within 6 weeks of the start of treatment.

Patient must meet all eligibility requirements to be entered onto the protocol.

5.3.1 Duration of Intervention and Evaluation:

Follow-up: A repeat CT scan will be performed after 2 cycles of treatment regimen to evaluate response based on RECIST 1.1 criteria (See Appendix 13.1 for definitions of response) (73). CT scans will be repeated at least every 2 cycles, or 8 weeks, to ensure no progression of disease. Patients will continue on VOR/HCQ or RGF until disease progression, unacceptable toxicity, withdrawal of consent by the patient, or decision of physician for patient's best interest. Crossover to the other arm will be allowed, but OPTIONAL, and will be determined by the treating physician for the patient's best interest. If patient is not given crossover treatment, then the patient will be off study and will be allowed to receive subsequent treatments. Each patient

will be followed for 1 year. We will follow the last patient for 12 months, at which time, the study will be completed for data analysis.

Interim analysis: The O'Brien-Fleming procedure will be used to conduct an interim analyses for efficacy when 50% of the patients complete the study. A statistical basis for stopping the study at the first look will be achieved if the test statistic indicates benefit in the VOR/HCQ Arm and exceeds 2.96259, corresponding to a significance level of 0.003. If the test statistic does not exceed 2.96259 at the first look then the trial will proceed to the final analysis. A treatment effect will be declared significant and beneficial at the final analysis if the test statistic indicates benefit and exceeds 1.96857, corresponding to a significance level of 0.047.

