Hepatic: AST increased (58% to 65%; grade 3: 3% to 5%; grade 4: 1%), ALT increased (39% to 45%; grade 3: 4% to 5%; grade 4: 1%), hyperbilirubinemia (33% to 45%)

Neuromuscular & skeletal: Stiffness (14%)

Renal: Proteinuria (33% to 60%; grade 3: 3%)

Miscellaneous: Infection (31% to 32%; grade ≥ 3 : 5% to 9%) 1%
to 10%:

Cardiovascular: Myocardial ischemia and infarction (1%)

Gastrointestinal: Taste disturbance (8%), xerostomia (5%), gastroesophageal reflux (1%)

Neuromuscular & skeletal: Tremor (2%)

Respiratory: Dyspnea (2%)

<1% (Limited to important or life-threatening): Bradycardia, erythema multiforme, gastrointestinal fistula, hypertensive crisis, liver injury (severe), liver failure, reversible posterior encephalopathy syndrome (RPLS), skin cancer (keratoacanthoma, squamous cell carcinoma), Stevens-Johnson syndrome, toxic epidermal necrolysis

Pregnancy Category D:

Risk Summary Based on its mechanism of action, Regorafenib can cause fetal harm when administered to a pregnant woman. There are no adequate and well-controlled studies with Regorafenib in pregnant women. Regorafenib was embryo lethal and teratogenic in rats and rabbits at exposures lower than human exposures at the recommended dose, with increased incidences of cardiovascular, genitourinary, and skeletal malformations. If this drug is used during pregnancy or if the patient becomes pregnant while taking this drug, the patient should be apprised of the potential hazard to a fetus

5.7 Primary and Secondary Endpoints: Primary endpoint:

- PFS-1: measured from the start of the first treatment the patient is randomized to until the date the criteria for progression are met or the date the patient is taken off study for any reason, whichever is shorter.

Secondary endpoints:

- OS: measured from the start of treatment on trial until the death of the patient.

- mPFS-2: measured from the start of the crossover treatment (OPTIONAL, second regimen) until the date the criteria for progression are met or the date the patient is taken off study for any reason, whichever is shorter.
- Response: measured as best response, complete response (CR) or partial response (PR), as defined by Response Evaluation Criteria in Solid Tumors (RECIST 1.1) Committee.
- Adverse events: grade 1-5 adverse events according to the National Cancer Institute Common Terminology Criteria for Adverse Events (NCI-CTCAE) v4.0; measured at baseline, each cycle, and at off study date.

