7.0 Data Collection

Data will be entered into Case Report Forms (CRF), which are currently in paper form.

For each patient on study, the following will be documented:

- Lab values: CBC, CMP, CEA, PTT/INR (when collected)
- PFS-1: measured from the start of the first treatment the patient is randomized to until the date the criteria for progression are met or the date the patient is taken off study for any reason, whichever is shorter).
- OS: measured from the start of treatment on trial until the death of the patient (date of death)
- PFS-2: measured from the start of the crossover treatment (Optional, second regimen) until the date the criteria for progression are met or the date the patient is taken off study for any reason, whichever is shorter.
- Response: measured as best response at any given time: complete response (CR) or partial response (PR), as defined by Response Evaluation Criteria in Solid Tumors (RECIST 1.1) Committee (73). (See Appendix 13.1 for definitions of response).
- Adverse events: the number and grade 1-5 of all adverse events will be documented according to the National Cancer Institute Common Terminology Criteria for Adverse Events (NCI-CTCAE) v4.0; measured at baseline, each cycle, and at off study date.

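### The comparative safety objective gets no between-arm estimate or confidence interval for severe toxicity, no rule for post-crossover events and no allowance for unequal treatment duration.

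*Combined protocol and SAP*

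**What the plan says.** Section 3.0 makes the safety objective comparative: "To further define the safety of the combination of VOR/HCQ when compared to RGF in treatment-refractory mCRC". Section 5.7 defines the endpoint as "grade 1-5 adverse events according to the National Cancer Institute Common Terminology Criteria", and Section 7.0 has the number and grade of events "measured at baseline, each cycle, and at off study date".

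Section 10.0 serves this objective with two listings (by type and grade; by treatment group and seriousness) and one comparison: "Treatments will be contrasted with regard to each adverse event with Fisher's Exact Test". The Synopsis plans only the listing by type and grade. In the same Section 10.0, PFS-1 gets a hazard ratio with a 95% CI and response gets an odds ratio with a 95% CI.

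Three other provisions bear on the comparison:

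- **Duration.** Section 5.3.1: "Patients will continue on VOR/HCQ or RGF until disease progression, unacceptable toxicity, withdrawal of consent by the patient", or until the physician decides otherwise. For the expected difference in duration, Section 10.0 starts from 1.9 months on RGF and states: "We predict VOR/HCQ will improve mPFS to 3.8 months".
- **Crossover.** The Synopsis allows optional crossover on study, after progression or unacceptable toxicity.
- **Collection window.** Section 8.0 documents events from first dose until 30 days after the last dose of study drug. It makes no break at crossover.

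**The concern.** A safety objective worded as a comparison would end in a list of separate p-values. None of them answers the first question a reader will ask: how much does severe toxicity differ between the arms, and how precisely is that known?

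Two features of the design make the omission more than cosmetic. First, a patient can receive both regimens on study, and Section 10.0 does not say whether an event on the second regimen counts, or for which arm. Second, if the trial's own hypothesis is right, VOR/HCQ patients stay on treatment about twice as long. A crude count over all treatment then gives that arm more time in which to record events.

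**Working it through.** **1. The plan's own figure.** The adverse event plan states no number, so its precision is set by the PFS-1 sample size. That size reproduces with the Freedman formula, two-sided alpha 0.05 (assumed) and HR = 1.9/3.8 = 0.5:

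- Events = [(1 + 0.5)/(1 − 0.5)]² × (1.960 + 0.842)² = 9 × 7.85 = 70.6, so 71.
- Probability of an event, with uniform accrual over 36 months plus 12 months of follow-up and exponential survival: 0.999 (RGF) and 0.983 (VOR/HCQ), mean 0.991.
- 71/0.991/2 = 35.8, so 36 per group; 36/0.95 = 37.9, so 38 per group.

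**2. What the per-event tests can show at 38 per arm.** If an event is absent in one arm, 5/38 in the other gives Fisher p = 0.054 and 6/38 gives p = 0.025. For grade 3 hand-foot syndrome at 17% (Section 2.2.1) v an assumed 1%, power is 0.53.

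**3. What a patient-level grade 3 or higher contrast would give.** The RGF rate is taken from the phase III trial described in Section 2.2.1: "54% patients had grade 3 or more adverse events versus 14% with placebo". The documents give no patient-level rate for VOR/HCQ, so a range is assumed. The half-width is 1.96 × √[0.54 × 0.46/38 + q(1 − q)/38].

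| Assumed VOR/HCQ rate q | Exact two-sided Fisher power | 95% half-width, points |
|---|---|---|
| 25% | 0.67 | 21.0 |
| 30% | 0.48 | 21.5 |
| 35% | 0.30 | 21.9 |
| 40% | 0.17 | 22.2 |

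Two examples with Newcombe intervals:

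- 21/38 v 11/38: 26 points (95% CI 4 to 45), Fisher p = 0.036.
- 21/38 v 15/38: 16 points (95% CI −6 to 36), p = 0.25.

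**4. Unequal exposure, constant toxicity hazard (assumed).** Let h be the monthly hazard of a first grade 3 or higher event and p the hazard of progression, with treatment running to progression and the 30-day tail ignored. Then p = ln2/1.9 = 0.365 on RGF and ln2/3.8 = 0.182 on VOR/HCQ, and the proportion with an event is h/(h + p).

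- RGF at 54%: h = 0.365 × 0.54/0.46 = 0.428.
- VOR/HCQ, same hazard: 0.428/(0.428 + 0.182) = 70%.
- VOR/HCQ, half the hazard: 0.214/(0.214 + 0.182) = 54%. The crude proportions are equal, and Fisher power is 0.03.

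In the half-hazard case, alternatives to the crude count behave as follows.

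- *Rate per patient-month.* Time at risk is 38/(h + p) = 47.9 v 95.8 patient-months, with 38 × 0.54 = 20.5 events in each arm. The rate ratio is 0.50, with 95% CI 0.50 × exp(±1.96 × √(2/20.5)) = 0.27 to 0.92. Simulated power over 20,000 trials is 0.60.
- *Proportion within 8 weeks (1.84 months).* If nobody stops early, 1 − exp(−1.84h) gives 55% v 33% (power 0.40). If patients stop at the PFS rates, h/(h + p) × [1 − exp(−1.84(h + p))] gives 41% v 28% (power 0.17).

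**5. Unequal exposure, toxicity confined to the first 8 weeks (equally assumed).** RGF is held at 54% and VOR/HCQ has half the hazard.

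- Nobody stops before the first CT: 1 − √0.46 = 32%, so 54% v 32% (power about 0.4).
- Stopping at the PFS rates: solving the formula in step 4 for 54% on RGF gives h = 0.647. Half of that with p = 0.182 gives 39%, so 54% v 39%.

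The crude count now shows most of the difference.

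**The case against.** The strongest reply is that this is a small reporting matter in a 76-patient phase II trial. Grade appears in the listings. Each Fisher test rests on a 2×2 table from which a risk difference can be computed, and severe toxicity drives the stopping rules in Section 8.0. Part of this stands: grade is not ignored, and the severity is low. But the stopping rules are monitoring thresholds, and the toxicity event they define is one due to VOR and/or HCQ; they compare nothing with RGF. Risk differences taken event by event also do not add up to a patient-level figure for severe toxicity.

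Several objections to stronger readings stand in full:

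- **Crossover.** A reader might infer that the plan charges post-crossover events to the original arm. No text says so. The handling is unspecified.
- **Grades tested.** A reader might infer from the grade 1-5 endpoint that each Fisher test counts any grade. Section 10.0 does not say which grades are counted.
- **Masking.** A reader might take 54% v 54% as a forecast that a real halving of toxicity would be hidden. It is algebra: halving both hazards leaves h/(h + p) unchanged. It needs a hazard constant over all treatment, which the documents do not support. Section 5.4.3 cuts the RGF dose after grade 3 events, and step 5 shows much less masking under early toxicity.
- **The 54%.** Section 2.2.1 gives no attribution for it, and the sentence before concerns treatment-related toxicity. It may not match an any-attribution endpoint.
- **An 8-week proportion as the main measure.** The window fits the scan schedule ("A repeat CT scan will be performed after 2 cycles of treatment regimen to evaluate response"). But once early stopping is allowed its power is 0.17 in the half-hazard model, and exposure stays unequal. It also closes before cumulative HCQ eye toxicity would appear; repeat eye examinations begin at 6 months (Section 6.0).

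**Conclusion.** The point holds as a minor gap in the analysis plan. A comparative secondary objective has no planned estimate or interval for severe toxicity, no rule for events after crossover, and no allowance for the difference in treatment duration that the design predicts.

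Its size is best stated as what is forgone: a risk difference known to about ±20 points, and a rate ratio with an interval such as 0.27 to 0.92. Neither assures power. Fisher power for the grade 3 or higher proportion runs from 0.67 down to 0.17 over assumed VOR/HCQ rates of 25% to 40%.

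The figures rest on 54% for RGF, assumed rates for VOR/HCQ, two-sided 0.05 and exponential times. The direction of the exposure problem follows from treatment to progression together with the assumed medians. Its size depends on when toxicity occurs, which the documents do not say. It should not be inferred that the primary result is at risk: PFS-1, the sample size and alpha are untouched.

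**What to change.** Add to the adverse events paragraph of Section 10.0, for all treated patients on the first regimen only and before any crossover:

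1. By arm, the proportion with at least one grade 3 or higher event (worst grade, any attribution), with the risk difference and 95% CI. Include patients who stop in Cycle 1, whom Section 10.0 already keeps evaluable for toxicity.
2. As the main exposure-adjusted comparison, first grade 3 or higher events per patient-month at risk, with the rate ratio and 95% CI. Time events by onset date or, if that is not captured, by cycle.
3. As a supporting summary, the proportion within 8 weeks of first dose.
4. The per-event Fisher tests as descriptive, stating which grades they count. Summarise events after crossover separately, by regimen received.

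The cost is a few sentences and no extra patients. Section 7.0 already records the number and grade of events each cycle, which is enough for timing by cycle; the documents do not show whether onset dates are captured.

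Downsides: intervals are wide at 38 per arm, and the rate ratio assumes a roughly constant hazard. If toxicity is mostly early, the extra low-risk months pull down the rate in the longer-treated arm, which is why items 1 and 3 should be shown beside it.
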